9.3.1 Pre-Vaccination Procedures (Visits 1 and 2)

1. Informed consent or ICF (Section 9.1.1; Visit 1 only).
2. Assessment of eligibility criteria (Section 7.1 and Section 7.2).
3. Demographics (Section 9.1.2; Visit 1 only).
4. Medical history (Section 9.1.2; Visit 1 only).
5. Medication/vaccination history (Section 9.1.2).
6. Randomization (Section 8.5; Visit 1 only).
7. Concomitant medications and vaccines (Section 9.1.2).
8. Documentation of trial entrance/randomization (Section 9.1.3; Visit 1 only).
9. Complete physical examination (Section 9.1.4).
10. Vital signs (Section 9.1.5).
11. Blood sampling (~ 3 mL) (Section 9.1.6).

9.3.2 Vaccination Procedures (Visits 1 and 2)

After completing all pre-vaccination procedures (Section 9.3.1), randomizing the subject at Visit 1 (Day 1), and assessing the criteria for the delay of trial vaccine administration, the investigator will administer the trial vaccine according to the procedures described in

CONFIDENTIAL

Section 8.5. At Visit 2 (Day 29-57 post-dose 1), it will be confirmed that the subject does not meet any criteria for delaying, or premature discontinuation of, additional trial vaccine administration, as described in Section 7.3.

9.3.3 Post-Vaccination Procedures (Visits 1 and 2)

The following post-vaccination procedures will be performed at Visits 1 and 2:

- Training of the subject's LAR on how to measure solicited local (injection site) reactions and body temperature, how to complete the diary card and how often to complete the diary card. Training should be directed at the individual(s) who will perform the measurements of solicited local (injection site) reactions and those who will enter the information on the diary card. This individual may or may not be the subject's LAR, but if a person other than the subject's LAR enters information on the diary card, this person's identity must be documented in the source documents and this person must receive training on the diary card. Training of this person on how to measure an injection site reaction, and how to take body temperature, and how to record the information on the diary card, should be performed while the subject is under observation after trial vaccine administration.

The diary card instructions must include the following:

- The individual(s) who will enter the information on the diary card must understand that timely completion of the diary card on a daily basis is a critical component of trial participation.

Please note:

The diary card will be the only source document allowed for remote collection of solicited local (injection site) reactions and systemic AEs (including body temperature measurements). The following additional rules apply to the documentation of safety information collected by diary card:

- The diary card should be reviewed with the subject's LAR.
- No corrections or additions to the diary card will be allowed after it is reviewed with the investigator/designee.
- Any blank fields on the diary card not otherwise corrected will be missing in the eCRF.
- Any newly described solicited safety information should be added to the diary card by the subject's LAR, and dated. Any new unsolicited safety information would be recorded in the subject's source document as a verbally-reported event and therefore captured as an AE and recorded in the AE eCRF.
- Starting on the day of trial vaccine administration, the subject's LAR will check for specific types of events at the injection site, any specific generalized symptoms (solicited systemic AEs), body temperature (rectal or axillary), any other symptoms or change in the subject's

health status, and any medications given to the subject (excluding vitamins and minerals). These solicited AEs and body temperature other symptoms and medications will be recorded on the diary card. Assessments should preferably take place in the evening.

- Temperature measurement is to be performed using the thermometer provided by the site. If the subject feels unusually hot or cold during the day, the subject's LAR should check their temperature. If the subject has fever, the highest body temperature observed that day should be recorded on the diary card.
- The measurements of solicited local (injection site) reactions are to be performed using the ruler provided by the site.
- The collection on the diary card of body temperature, solicited local (injection site) reactions, and solicited systemic AEs will continue for a total of 7 days after each trial vaccine administration (Visits 1 and 2). The collection on the diary card of unsolicited AEs and concomitant medications and vaccines will continue for 28 days after trial vaccine administration.

After trial vaccine administration, the subject will be observed for at least 30 minutes including observation for unsolicited AEs, solicited local (injection site) reactions, and solicited systemic AEs and body temperature measurement. Information should be recorded in the eCRF. The investigator or delegate will take the opportunity to remind the subject's LAR how to measure solicited local (injection site) reactions and body temperature as part of this observation period. All safety data will be collected in the subject's source documents.

The site staff should schedule the next trial activity reminder call or visit.

The subject's LAR will receive a written reminder of the next planned trial activity. The subject's LAR will be reminded to complete the diary card daily and to contact the site if there are any questions and to contact the site immediately (or as soon as the subject is medically stable) if the subject has a medical condition that leads to a hospitalization or an emergency room visit. All contact details will be provided to the subject's LAR.

9.3.4 Phone Contacts - Reminder Calls (2 and 7 days post-vaccination)

Post-vaccination reminder phone calls (or text messages) will be performed on 2 and 7 days post each dose. The purpose is to remind the subject's LAR about completion of the diary card. If the subject's LAR wishes to describe safety information, this information should only be collected by a trained healthcare professional at the site, and the safety data described must be recorded in source documents. The subject's LAR should be reminded to record the information on the diary card and to contact the site via the telephone number provided in the ICF to discuss medical questions.

9.3.5 Site Visits After Vaccination (Visit 3)

A site visit that does not include a trial vaccine administration will occur at 28 days (Visit 3) post-dose 2. Procedures include targeted physical examination, vital signs, diary card review, concomitant medications and vaccinations and blood draw. The healthcare professional reviewing these data will discuss the AEs (if any) reported by the subject's LAR and will determine if any additional diagnoses and/or AEs are present and/or if concomitant medications and vaccinations have been administered.

Blood (~ 3 mL) should be taken from the subject using an aseptic venipuncture technique for serological immunogenicity testing.

At Visit 3, the site staff should schedule the next site visit or other trial activity with the subject's LAR.

The subject's LAR will receive a written reminder of the next planned trial activity. The subject's LAR will be reminded to contact the site if there are any questions and to contact the site immediately (or as soon as the subject is medically stable) if the subject has a medical condition that leads to a hospitalization or an emergency room visit.

9.3.6 Final (End of Trial) Visit (Visit 4)

The final (end of trial) visit will be performed at 6 months (Day 180) post-dose 2. Procedures include targeted physical examination, vital signs, and blood draw (~ 3 mL; should be taken from the subject using an aseptic venipuncture technique for serological immunogenicity testing). At Visit 4, the healthcare professional will determine if additional MAAEs or SAEs not already made known to the site occurred after Visit 3, and if concomitant medications and vaccines were used. If a subject terminates earlier, the final (end of trial) visit procedures should be performed at their last trial visit, if possible. The investigator must complete the End of Trial eCRF page for all subjects who received the trial vaccine.

9.3.7 Post-Trial Care

No post-trial care will be provided.

9.4 Biological Sample Retention and Destruction

In this trial, specimens for immune response testing will be collected as described in Section 9.1.6. After blood draw and serum processing, the serum samples will be preserved and retained at a central laboratory that was contracted by the sponsor for this purpose for up to but not longer than 20 years or as required by applicable law. The sponsor has put into place a system to protect the subject's personal information to ensure optimal confidentiality and defined standard processes for sample and data collection, storage, analysis, and destruction.

Serum samples will be used for the analyses defined in this protocol, but can also, with permission from subject's LAR, be used to assess, improve, or develop tests related to norovirus

or the trial vaccine that will allow more reliable measurement of the response to the trial vaccine. Serum samples could also be used for further exploratory testing. If the subject's LAR does not consent to future testing of samples on the ICF, the subject can still participate in the trial.

10.0 ADVERSE EVENTS

10.1 Definitions

10.1.1 Adverse Events

An AE is defined as any untoward medical occurrence in a clinical investigation subject administered a trial vaccine; it does not necessarily have to have a causal relationship with trial vaccine administration.

An AE can therefore be any unfavorable and unintended sign (e.g., a clinically significant abnormal laboratory finding), symptom, or disease temporally associated with the administration of a trial vaccine whether or not it is considered related to the trial vaccine.

AEs will be graded by the investigator in the following manner:

Mild	Grade 1	
• Awareness of symptoms that are easily tolerated, causing minimal discomfort and not interfering with everyday activities. Relieved with or without symptomatic treatment.
Moderate	Grade 2	
• Sufficient discomfort is present to cause interference with normal activity. Only partially relieved with symptomatic treatment.
Severe	Grade 3	
• Extreme distress, causing significant impairment of functioning or incapacitation. Prevents normal everyday activities. Not relieved with symptomatic treatment.

10.1.2 Solicited Adverse Events

The occurrence of selected indicators of safety will be measured/collected for 7 days after administration of trial vaccine (including the day of administration), at Visits 1 and 2, and will be recorded on the AE eCRF page as applicable and as listed in Table 10.a.

Any solicited local reactions or systemic AEs observed as continuing on Day 8 after the trial vaccine administration will be recorded as an AE on the AE eCRF for follow-up. For these persistent/prolonged solicited AEs the end date will be captured on the AE eCRF to permit a separate analysis from the unsolicited AEs (see Section 10.4.2).

Table 10.a Solicited Local (Injection Site) Reactions and Systemic AEs

Solicited local (injection site) reactions:	Pain Erythema Induration Swelling
Systemic adverse events:	Drowsiness Irritability/fussiness Loss of appetite Fever* Vomiting Diarrhea

Body temperature will be collected and recorded. *Fever is defined as body temperature $\geq 38^{\circ}\text{C}$ (100.4°F) regardless of method used [28].

The intensity of solicited safety parameters will be assessed as described in Table 10.b.

Table 10.b Solicited Safety Parameters

Adverse Event	Intensity Grade	Intensity
Pain at injection site	0	None
	1	Mild: Minor reaction to touch
	2	Moderate: Cries/protests on touch
	3	Severe: Cries when limb is moved/spontaneously painful
Erythema at injection site ^(a)	0	≤ 10 mm
	1	Mild: $>10 - \leq 20$ mm
	2	Moderate: $>20 - \leq 40$ mm
	3	Severe: >40 mm
Induration at injection site ^(a)	0	≤ 10 mm
	1	Mild: $>10 - \leq 20$ mm
	2	Moderate: $>20 - \leq 40$ mm
	3	Severe: >40 mm
Swelling at injection site ^(a)	0	≤ 10 mm
	1	Mild: $>10 - \leq 20$ mm
	2	Moderate: $>20 - \leq 40$ mm
	3	Severe: >40 mm
Drowsiness	0	Behavior as usual
	1	Mild: Drowsiness easily tolerated
	2	Moderate: Drowsiness that interferes with normal activity
	3	Severe: Drowsiness that prevents normal activity
Irritability/fussiness	0	Behavior as usual
	1	Mild: Crying more than usual/no effect on normal activity
	2	Moderate: Crying more than usual/interferes with normal activity
	3	Severe: Crying that cannot be comforted/prevents normal activity
Loss of appetite	0	Appetite as usual
	1	Mild: Eating less than usual/no effect on normal activity
	2	Moderate: Eating less than usual/interferes with normal activity
	3	Severe: Not eating at all
Vomiting	0	None
	1	Mild: No interference with activity or 1 – 2 episodes/24h
	2	Moderate: Some interference with activity or >2 episodes/24h
	3	Severe: Prevents activity, requires outpatient IV hydration
Diarrhea	0	None
	1	Mild: 2 – 3 loose stools/24h
	2	Moderate: 4 – 5 loose stools/24h
	3	Severe: ≥ 6 watery stools/24h or requires outpatient IV hydration
Fever ^(b)	Record body temperature in °C/°F	

Abbreviations: h, hour; IV, intravenous.

(a) Subject's LAR to record greatest surface diameter in mm on the diary card.

(b) Fever is defined as body temperature $\geq 38^{\circ}\text{C}$ (100.4°F) regardless of method used [28].

10.1.3 Adverse Events of Special Interest

Not applicable. No adverse event of special interest (AESI) has been identified for this trial.

CONFIDENTIAL

10.1.4 Medically-attended Adverse Events

An MAAE is defined as an AE leading to an unscheduled visit to or by a healthcare professional including visits to an emergency department, but not fulfilling seriousness criteria.

10.1.5 Serious Adverse Events

An SAE is defined as any untoward medical occurrence that:

1. Results in DEATH.
2. Is LIFE THREATENING.
 - The term life threatening refers to an event in which the subject was at risk of death at the time of the event; it does not refer to an event that hypothetically might have caused death if it were more severe.
3. Requires inpatient HOSPITALIZATION or prolongation of existing hospitalization.
4. Results in persistent or significant DISABILITY/INCAPACITY.
5. Leads to a CONGENITAL ANOMALY/BIRTH DEFECT in the offspring of a subject.
6. Is an IMPORTANT MEDICAL EVENT that satisfies any of the following:
 - May require intervention to prevent items 1 to 5 above.
 - May expose the subject to danger, even though the event is not immediately life threatening or fatal or does not result in hospitalization.

10.2 Causality of Adverse Events

Relationship (causality) to the trial vaccine will also be assessed by the investigator. The relationship of each AE to the trial vaccine, including solicited systemic AEs (solicited local reactions are considered as related by default) will be assessed using the following categories:

Related: There is suspicion that there is a relationship between the trial vaccine and the AE (without determining the extent of probability); there is a reasonable possibility that the trial vaccine contributed to the AE.

Not Related: There is no suspicion that there is a relationship between the trial vaccine and the AE; there are other more likely causes and administration of the trial vaccine is not suspected to have contributed to the AE.

10.2.1 Relationship to Trial Procedures

Relationship (causality) to trial procedures should be determined for all AEs.

The relationship should be assessed as related to trial procedure if the investigator considers that there is a reasonable possibility that an event is due to a trial procedure. Otherwise, the relationship should be assessed as not related.

10.2.2 Outcome of Adverse Events

The outcome of AEs can be described as follows:

Resolved: The subject has fully recovered from the event or the condition has returned to the level observed at baseline.

Resolving: The event is improving but the subject is still not fully recovered.

Not resolved: The event is ongoing at the time of reporting and the subject has still not recovered.

Resolved with sequelae: As a result of the AE, the subject suffered persistent and significant disability/incapacity (e.g., became blind, deaf or paralysed).

Fatal: The subject died due to the event. If the subject died due to other circumstances than the event, the outcome of the event per se should be stated otherwise (e.g., not resolved or resolving).

Unknown: If outcome is not known or not reported.

10.3 Additional Points to Consider for Adverse Events

An untoward occurrence generally may:

- Indicate a new diagnosis or unexpected worsening of a pre-existing condition. Intermittent events for pre-existing conditions or underlying disease should not be considered as AEs.
- Necessitate therapeutic intervention.
- Require an invasive diagnostic procedure.
- Require trial vaccine discontinuation or a change in concomitant medication.
- Be considered unfavorable by the investigator for any reason.

Diagnoses *vs.* signs and symptoms:

- Each event should be recorded to represent a single diagnosis. Accompanying signs (including abnormal laboratory values) or symptoms should NOT be recorded as additional AEs. If a diagnosis is unknown, signs or symptoms should be recorded appropriately as AEs.

Worsening of AEs:

- If the subject experiences a worsening or complication of an AE after administration of the trial vaccine, the worsening or complication should be recorded as a new AE. Investigators should ensure that the AE term recorded captures the change in the condition (e.g., worsening of...).

- If the subject experiences a worsening or complication of an AE, the worsening or complication should be recorded as a new AE. Investigators should ensure that the AE term recorded captures the change in the condition (e.g., worsening of...).

Changes in intensity of AEs:

- If the subject experiences changes in intensity of an AE, the event should be captured once with the maximum intensity recorded.

Preplanned surgeries or procedures:

- Preplanned procedures (surgeries or therapies) that were scheduled prior to signing of the ICF are not considered as AEs. Complications resulting from any planned surgery should be reported as AEs.

Elective surgeries or procedures:

- Elective procedures performed where there is no change in the subject's medical condition should not be recorded as AEs, but should be documented in the subject's source documents. Complications resulting from an elective surgery should be reported as AEs.

Trial procedures:

- Adverse occurrences related to trial procedures after signing of the ICF are considered as AEs and should be reported as AEs.

Other:

- If possible, include anatomical location to the AE verbatim.
- Death is the outcome of an AE, not the AE term.
- Cause of death is the AE term.

10.4 Collection and Reporting Procedures

10.4.1 Collection and Reporting of Adverse Events

All AEs, whether considered related to the use of the trial vaccine or not, must be monitored by the investigator until symptoms subside and any abnormal laboratory values have returned to baseline, or until there is a satisfactory explanation for the changes observed, or until death, in which case a full autopsy report should be supplied, if possible. All findings must be reported on the AE eCRF form, if necessary (see Section 10.4.4). All findings in a subject experiencing an AE must also be documented in that subject's source documents. Any unsolicited AE will be collected by the subject's LAR or designated person for 28 days post-dose via the diary card as a memory aid for reporting to the site at the subsequent clinic visit (Visit 2 or Visit 3). AEs leading to trial vaccine discontinuation will be collected up to the second trial vaccine dose administration and AEs leading to withdrawal from the trial will be collected throughout the trial. Even if the subject is deemed ineligible to receive further doses of trial vaccine, all efforts

should be made to continue the collection of safety data according to the protocol.

The following information will be documented for each event:

- Reported term for the AE.
- Start and end date, duration.
- Serious (Y/N).
- Intensity.
- Investigator's opinion of the causality (relationship) between the event and administration of trial vaccine (related or not related).
- Investigator's opinion of the causality (relationship) to trial procedure(s), including the details of the suspected procedure.
- Action taken with the trial vaccine.
- Outcome of event.

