5.0 TRIAL OBJECTIVES, ENDPOINTS AND SUMMARY MEASURES

Primary Objective	Endpoints	Summary Measures

 To assess the safety of HIL-214 compared to placebo. 	
 Occurrence and intensity of solicited local reactions up to 7 days after each dose of trial vaccine. Occurrence, intensity, and relationship of solicited systemic AEs up to 7 days after each dose of trial vaccine. Occurrence, intensity, and relationship of unsolicited AEs up to 28 days after each dose of trial vaccine. Occurrence, intensity, and relationship of AEs leading to withdrawal of trial vaccine up to 56 days post-dose 1. 	Number of, and proportion of subjects with: 
 Solicited local reactions* up to 7 days post-dose 1 and dose 2. Solicited systemic AEs** up to 7 days post-dose 1 and dose 2. Unsolicited AEs up to 28 days post-dose 1 and dose 2. AEs leading to withdrawal of trial vaccine up to 56 days post-dose 1. In the SAF.
Secondary Objectives		
Safety		
	
 To further assess the safety of HIL-214 compared to placebo. 	
 Occurrence, intensity, and relationship of AEs leading to withdrawal from the trial, SAEs and MAAEs throughout the entire trial period
Immunogenicity		
	
 To assess the immunogenicity of HIL-214. 	At baseline, pre-dose 2, and 28 days post-dose 2 and 6 months post-dose 2: 
 HBGA blocking antibody titers. Pan-Ig antibody titers.
		
 SRR *** for GII.1 titers pre-dose 2 and 28 days post-dose 2. SRR *** for GII.4 titers pre-dose 2 and 28 days post-dose 2. GI.1 GMFs at baseline, pre-dose 2, 28 days post-dose 2 and 6 months post-dose 2. GI.4 GMFs at baseline, pre-dose 2, 28 days post-dose 2 and 6 months post-dose 2. GI.1 GMFR from baseline to pre-dose 2, 28 days post-dose 2 and 6 months post-dose 2. GI.4 GMFR from baseline to pre-dose 2, 28 days post-dose 2 and 6 months post-dose 2.
		In the PPS. Selected analyses may be provided using the FAS.

Abbreviations and notes on the next page.

CONFIDENTIAL

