13.1.4 Safety Analyses

All safety data analyses will be performed using the SAF. Summaries will be provided for each trial arm and overall.

Solicited AEs

Solicited AEs will be assessed during 30 minutes after administration of each dose of trial vaccine and then daily for 7 days (including the day of administration). For each solicited AE, the number and percentage of subjects will be computed, for each day from Day 1 to Day 7 after each trial vaccine dose administration (including the day of trial vaccine administration) and overall.

Solicited AEs will be summarized by intensity and, for systemic events, by relationship to the trial vaccine. For subjects with more than 1 episode of the same event within an interval, the maximum intensity and strongest relationship will be used for tabulations.

Body temperature measurements will be summarized in categories (including fever, defined as temperature $\geq 38^{\circ}\text{C}$), without adjustment for the route of measurement. Summaries of the day of first onset of each event and the number of days subjects experienced each event will also be provided.

Data from the 30 minutes assessment will be summarized separately.

Unsolicited AEs

Any unsolicited AEs, SAEs, MAAEs, and AEs leading to trial vaccine or trial withdrawal, will be coded using MedDRA, and summarized by system organ class (SOC) and preferred term (PT) using number and percentage of subject with an AE. Subjects with more than one occurrence for the term will be counted only once for this term.

For any unsolicited AEs, collected up to 28 days after administration of each dose of trial vaccine (including the day of administration), summaries will also be provided by event intensity (mild, moderate, severe) and relationship (not related, related) to trial vaccine or trial procedures. For subjects with more than one AE within a SOC or PT, then the AE with the maximum intensity or strongest relationship within each SOC and each PT will be included in the summaries by intensity or relationship, respectively.

Any unsolicited AEs will be summarized in the following 3 time intervals: 1) overall up to 28 days after trial vaccine administration, 2) with onset between 1 and 7 days after each dose

(including the day of trial vaccine administration), and 3) with onset between 8 and 29 days after each dose (including the day of trial vaccine administration).

AEs leading to trial vaccine withdrawal

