## 7.2. Study Vaccine

Subjects will receive the first vaccine at Visit 1 (Study Day 1) and the second vaccine at Visit 2 (between Study Day 29 to 57). The date and time of administration, kit number, injection site and whether the subject was observed for 30 minutes post injection will all be collected on the CRF. Additionally, whether the dose was delayed and reason for delay will be recorded in the subject's CRF.

The number of subjects who received both doses, a summary of the time between both doses in days and the day of dose 2 administration will be summarized on the SAF.

All study vaccine administration data will be presented in a data listing.

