## **9.2. Unsolicited Adverse Events**

An AE is defined as any untoward medical occurrence in a clinical investigation subject administered a trial vaccine; it does not necessarily have to have a causal relationship with trial vaccine administration. An AE can therefore be any unfavorable and unintended sign (e.g., a clinically significant abnormal laboratory finding), symptom, or disease temporally associated with the administration of a trial vaccine whether or not it is considered related to the trial vaccine.

Unsolicited AEs are collected through 28 days post-first and second vaccination. AEs leading to trial vaccine withdrawal are collected up to the second trial vaccine dose administration. SAEs, AEs leading to withdrawal from trial and MAAEs are collected for the entire study period.

The reported term for the unsolicited AE, start and end date, seriousness, severity, relationship to trial vaccine or trial procedure, action taken and outcome of event will be collected on the eCRF.

Summaries of the total number of unsolicited AEs and the number and percentage of subjects with at least one AE will be provided by trial arm. AEs will be presented by SOC and PT. At each level of subject summarization, a subject is counted once if the subject reported one or more events. Percentages will be calculated out of the number of subjects in the SAF. The summary of AEs will be presented in descending order from the SOC with the highest total incidence to the SOC with the lowest total incidence. If the total incidence for any two or more SOCs is equal, the SOCs will be presented in alphabetical order. Within each SOC, the PTs will be presented in alphabetical order.

Summaries of unsolicited AEs will be presented as follows after both vaccines (individually and combined):

1. Overall up to 28 days after trial vaccine administration;
2. With onset between Day 1 and Day 7 after each dose (including the day of trial vaccine administration);
3. With onset between Day 8 and Day 29 after each dose (including the day of trial vaccine administration).

Any AE reported between Day 29 and the second vaccination (up to Day 57) will be included in the listed.

Unsolicited AEs will be coded by PT and SOC using the latest MedDRA version.

For missing/partial start and end dates, the rules stated in Section 4 will be followed.

All AEs will be presented in a listing.

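### With AE dates only and the whole dosing day counted as post-dose, some events that precede the injection are tabulated as post-vaccination AEs (minor)

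*Protocol*

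**What the plan says.** **What is recorded for an AE.** Protocol 10.4.1 lists, as the timing item, "Start and end date, duration". SAP 9.2 gives the eCRF content as "The reported term for the unsolicited AE, start and end date, seriousness, severity, relationship to trial vaccine or trial procedure", followed by action taken and outcome. Neither list has an onset time or a mark for before or after injection. For the vaccine itself, SAP 7.2 does collect a time: "The date and time of administration, kit number, injection site".

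**What is counted.** The primary endpoint in protocol 5.0 includes "Occurrence, intensity, and relationship of unsolicited AEs up to 28 days after each dose of trial vaccine". Protocol 13.1.4 describes these events as "collected up to 28 days after administration of each dose of trial vaccine (including the day of administration"). The SAP 9.2 sub-window reads "With onset between Day 1 and Day 7 after each dose (including the day of trial vaccine administration").

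**What happens before the injection.** Protocol 9.3.1 places the physical examination, vital signs and "Blood sampling (~ 3 mL) (Section 9.1.6") among the pre-vaccination steps at both Visit 1 and Visit 2.

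**Rules that separate pre-injection events.** Protocol 9.1.2 sends occurrences between consent and the first dose to the medical history page, except those judged related to a screening procedure, which are recorded as AEs. Protocol 10.3 is wider on procedures: "Adverse occurrences related to trial procedures after signing of the ICF are considered as AEs and should be reported as AEs". SAP 9.2 says that AEs arising between Day 29 and the second vaccination go in the listing.

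**The concern.** Each dosing day has a period before the injection that contains an invasive procedure. The plan means to keep some pre-injection events out of the post-dose tables: 9.1.2 does this before dose 1, and the SAP listing rule does it before dose 2. When an AE starts on the dosing day, its date cannot show which side of the injection it falls on, and the window rule then counts it as post-dose.

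At stake is whether the counts in a primary safety endpoint mean what their label says. The arms have 14 and 7 infants, so a single misplaced infant is visible in the percentages.

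**Working it through.** The plan states no figure on this point, so there is none to reproduce. The check traces the rules and then sizes one misplaced infant.

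**Step 1. Follow each type of event through the rules.** Dose 2 is given 28 to 56 days after dose 1, which is Study Day 28 + 1 = 29 to 56 + 1 = 57.

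| Event, with onset before the injection | Where the rules put it | Counted as post-dose? |
|---|---|---|
| Visit 1, not procedure-related | Medical history (9.1.2) | No |
| Visit 1, related to the pre-dose draw | AE dated Day 1 (9.1.2, 10.3) | Yes, dose 1 Day 1 |
| Visit 2 on Study Day 29, any new AE | AE dated Day 29 | Yes, dose 2 Day 1; the date also lies in the dose 1 Day 8–29 window |
| Visit 2 on Study Days 30–57, any new AE | Listing only by intent (SAP 9.2) | Yes, because its date is dose 2 Day 1 |

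The second row assumes that the pre-dose draw is treated as a screening or trial procedure. In the third row only the dose 2 table is wrong: the event belongs to the dose 1 window, so the combined count is right. In the fourth row the combined count is raised as well.

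**Step 2. Check whether other recorded items correct this.** The injection time has no AE time to be compared with. Protocol 10.4.1 also records the suspected procedure, and SAP 9.2.1 summarizes relationship to procedure. That identifies draw-related AEs but removes none from the counts, and it does not help with an unrelated event that began before dose 2.

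**Step 3. Size of one misplaced infant.** SAP 9.2 counts each subject once per level of summary, so a percentage moves only if the infant has no other AE at that level and window.

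- HIL-214: 1/14 = 7.1 points
- Placebo: 1/7 = 14.3 points
- Overall: 1/21 = 4.8 points

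**Step 4. Frequency, by assumption only.** Let q be the chance of a recorded pre-injection AE per dosing day. The documents give no value. If all 21 infants receive dose 2, the chance of at least one such event on a dose 2 day is 1 − (1 − q)^21:

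| Assumed q | At least one on the 21 dose 2 days | Expected number (21q) |
|---|---|---|
| 1% | 19% | 0.21 |
| 2% | 35% | 0.42 |
| 5% | 66% | 1.05 |
| 10% | 89% | 2.10 |

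Over all 42 dosing days the same formula gives 34%, 57%, 88% and 99%. Those are upper bounds, because ordinary pre-injection events on Day 1 are not counted. Both sets of figures restate the assumed q and are not evidence of how often it happens.

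**Step 5. Effect on the comparison.** Suppose an infant has true post-dose AE probability p1 (HIL-214) or p0 (placebo), and an independent added probability b of a misplaced AE, equal in both arms. The observed difference is [1 − (1 − p1)(1 − b)] − [1 − (1 − p0)(1 − b)] = (1 − b)(p1 − p0). With b = 5% the difference keeps 95% of its size; with b = 10%, 90%.

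**The case against.** The strongest reply is that little is left once the plan's own safeguards are applied.

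- **Visit 1.** A reader might infer that every event before the first injection is counted. The documents do not support this: 9.1.2 sends all but procedure-related events to medical history.
- **Visit 2.** A reader might infer that nothing separates events before dose 2. SAP 9.2 does have a rule, the listing of AEs between Day 29 and dose 2. What is missing is the item needed to apply it on the dosing day itself.
- **Illness on the morning of dose 2.** Delay criteria are checked before each dose (schedule footnote c; 7.3), and they include clinically significant active infection and fever. If the dose is delayed, that day is not a dosing day. This stands, and it leaves mostly minor events.
- **Draw-related events.** The suspected procedure is already recorded, so these can be identified. This also stands. A bruise from the draw may appear only after the injection, so a before/after item would miss it and the procedure item is the better tool.
- **The comparison between arms.** A reader might infer a biased contrast or a distorted reactogenicity picture. Both arms have the same pre-dose procedures, the shrinkage in Step 5 is modest, the trial is descriptive, and reactogenicity is read from the separate solicited AE tables.
- **The eCRF.** It is not among the documents, and the AE lists are not exhaustive: SAP 9.2.6 uses a study-discontinuation item that appears in neither. A time field may exist. Even so, the SAP has no rule that uses one.

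The two misassigned groups and the listing rule that dates cannot resolve are still there after these points.

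**Conclusion.** The point holds for two groups: procedure-related AEs before dose 1, and any new AE that begins on the dose 2 day before the injection. By the stated rules both are tabulated as post-dose in a primary endpoint. It does not extend to other pre-injection events on Day 1.

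Severity is minor. The events are mostly minor and similar in both arms. One infant moves an arm's percentage by at most 7.1 points (HIL-214) or 14.3 points (placebo), and only if that infant has no other AE in the window. The frequency is not known from the documents. The conclusion assumes that the eCRF holds no more timing detail than 10.4.1 and SAP 9.2 list, and that the pre-dose draw is treated as a screening or trial procedure.

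**What to change.** 1. **Protocol 10.4.1 and AE eCRF.** For AEs that start on a dosing day only, record whether onset was before or after the injection, or record the onset time. If data are already collected, classify these AEs blind from source documents before unblinding.
2. **SAP 9.2.** Count a dosing-day AE as post-dose only if its onset is at or after the injection. Place a pre-injection AE on the dose 2 day in the dose 1 window if it falls within that window, and otherwise in the listing.
3. **SAP 9.2.1.** Use the recorded suspected procedure to show AEs attributed to the pre-dose blood draw on a separate row, whatever their onset time.

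The cost is one extra item for sites, needed only for dosing-day AEs, and a short addition to the SAP and table shells.
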